7.3 PLANNED ANALYSES

7.3.1 Primary analyses

The pharmacokinetic parameters AUC_{0-tz} and C_{max} will be log-transformed (natural logarithm) prior to fitting the ANOVA model. The difference between the expected means for $\log(T)-\log(R)$ will be estimated by the difference in the corresponding Least Square Means (point estimate) and 2-sided 90% confidence intervals based on the t-distribution will be computed. These quantities will then be back-transformed to the original scale to give the point estimator and interval estimates for the geometric mean intra-subject ratio between response under test and response under reference.

All evaluable subjects who received at least one dose of volasertib will be included in the pharmacokinetic analysis. Subjects who are considered as not evaluable will be listed with their individual plasma concentrations and individual pharmacokinetic parameters, however, will not be included in descriptive statistics for plasma concentrations, pharmacokinetic parameters or other statistical assessment.

Concentrations will be used for graphs and calculations in the format that is reported in the bioanalytical report. Noncompartmental pharmacokinetic analyses of the plasma concentration-time data will be performed using a validated software program, e.g. Winnonlin Version 5.2. Only concentrations within the validated concentration range will be used for the calculation of pharmacokinetic parameters. For pre-dose samples, the actual sampling time will be set to zero.

Plasma concentrations will be plotted graphically versus time for all evaluable subjects as listed in the drug plasma concentration-time tables. For the presentation of the mean profiles, the geometric and arithmetic mean and the planned blood sampling times will be used. If the actual sampling time deviates significantly from the planned time, the corresponding plasma concentration will be excluded from the calculation of descriptive statistics.

The following descriptive statistics will be calculated for analyte concentrations as well as for all pharmacokinetic parameters: N, arithmetic mean, standard deviation, minimum, median, maximum, arithmetic coefficient of variation, geometric mean, and geometric coefficient of variation. The data format for descriptive statistics of concentrations will be identical with the data format of the respective concentrations. The descriptive statistics of pharmacokinetic parameters will be calculated using the individual values with the number of decimal places as provided by the evaluation program. Then the individual values as well as the descriptive statistics will be reported with three significant digits in the clinical trial report.

Proprietary confidential information.

© 2017 Boehringer Ingelheim International GmbH or one or more of its affiliated companies. All rights reserved.
This document may not - in full or in part - be passed on, reproduced, published or otherwise used without prior written permission.

7.3.2 Secondary analyses

7.3.2.1 Secondary pharmacokinetic parameters

Relative bioavailability will not be assessed for secondary pharmacokinetic parameters. Apart from this, the same methods as described for primary pharmacokinetic endpoints will be used to analyse the secondary endpoints.

7.3.2.2 Safety and tolerability analyses

Refer to section 7.3.3 for a description of the analysis of safety and tolerability.

7.3.3 Safety analyses

All patients who receive at least one dose of study drug will be included in the safety evaluation. Safety analyses will be performed in accordance with BI standards.

Adverse events will be coded using the Medical Dictionary for Drug Regulatory Activities (MedDRA). Adverse events occurring prior to drug administration will be assigned to the screening period. Adverse events occurring within 21 days of most recent volasertib infusion will be considered to be on treatment.

Independent of this rule, the relationship of an adverse event to the study drug treatments will be assessed by the investigator. Adverse event information as reported in the eCRFs will be aggregated in a two step process. First, multiple recordings (AE occurrences) of the same adverse event will be combined into one AE episode (collapsing). The second step will combine all of the AE episodes of an adverse event into one AE record as needed for by-patient summaries (condensing).

Reporting of adverse events and laboratory data will follow the standard BI procedures. The analysis of adverse events will comprise various frequency tabulations. Tables will be produced for treatment cycle 1 (co-administration of volasertib and itraconazole), treatment cycle 2 (volasertib alone) and for all treatment cycles combined. DRTs and the MTD (see [Section 5.2.6](#)) will be reported.

Laboratory values will be listed, tabulated and compared with their reference ranges. They will also be assessed with regard to possible changes compared to baseline values and with regard to the comparison of the first and second treatment cycle. The frequency of possible clinically significant abnormalities will be tabulated.

Safety will also be assessed by evaluation of physical examination (see [Section 7.3.8](#)), vital signs (blood pressure, pulse rate) and 12-lead ECG. Change from screening and/or baseline as well as change between treatment cycle 1 and 2 will be compared descriptively.

7.3.4 Interim analyses

[figure not shown]
No formal interim analysis is planned. However a review of all data relevant for safety will be performed after the first three patients were included. In case of unacceptable toxicity, the dose of drug might be reduced to 250 mg or 200 mg according to the dose deescalation scheme in [Section 3.1](#). Therefore, reviews of safety will be performed after cohorts of three patients have been dosed.

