4.1.3.1 Potential dose reduction

Reduction of starting dose

Initially, patients will be treated sequentially. Single patients will be treated for the first cycle until three patients have completed the first cycle.

Thereafter, cohorts of 3 patients will be treated until the preliminary safety of volasertib in combination with itraconazole is confirmed.

If more than 1 out of 6 patients experiences unacceptable toxicity (DRT, Section 5.2.6) during the first treatment cycle, the dose of volasertib for subsequent patients will be deescalated to 250 mg in the first and second treatment period.

If more than 1 out of 6 patients treated at a volasertib dose of 250 mg experiences unacceptable toxicity during the first treatment cycle, the dose of volasertib for subsequent patients will be further deescalated to 200 mg in the first and second treatment period.

The highest dose for which the incidence of unacceptable toxicity is no more than 1 out of 6 will be used as the dose of volasertib for the first and second treatment cycle of all further patients included in the trial (MTD, cf. [Section 5.2.6](#)).

Dose reduction in individual patients

If a patient experiences unacceptable toxicity (DRT, Section 5.2.6) the patient can continue volasertib treatment at a lower dose if criteria for retreatment are met (see [Section 3.3.5](#)). Each occurrence of DRT will lead to a dose reduction by 50 mg of any subsequent volasertib infusion(s). No dose reduction of volasertib below 200 mg is allowed.

If a patient experiences a DRT at the 200 mg dose, i.e. a dose reduction to <200 mg would be required, the volasertib treatment will be permanently discontinued and the patient will move to the EoT visit.

Proprietary confidential information.

© 2017 Boehringer Ingelheim International GmbH or one or more of its affiliated companies. All rights reserved.
This document may not - in full or in part - be passed on, reproduced, published or otherwise used without prior written permission.

When a dose reduction of volasertib occurs, this applies to all subsequent cycles with no possibility to dose escalation back to the previous dose.

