5.2.3 Assessment of safety laboratory parameters

Blood samples will be collected from venous blood at the time points indicated in the [flow chart](#). Laboratory tests listed will be performed at the study sites and may be performed within 2 days prior to the visit day to allow a rapid decision whether the patient may be eligible for further therapy or not. All reference values of laboratory tests performed at study site should be provided to Boehringer Ingelheim.

Laboratory tests will include the parameters listed in [Table 5.2.3:1](#).

Proprietary confidential information.

© 2017 Boehringer Ingelheim International GmbH or one or more of its affiliated companies. All rights reserved.
This document may not - in full or in part - be passed on, reproduced, published or otherwise used without prior written permission.

Table 5.2.3:1

Laboratory tests

Hematology	red blood cell count (RBC), haemoglobin, hematocrit, medium corpuscular volume (MCV), white blood cell count (WBC) with differential count, and platelets
Biochemistry	glucose, sodium, potassium, calcium, creatinine, aspartate amino transferase (AST), alanine amino transferase (ALT), alkaline phosphatase, gamma-glutamyl transferase (GGT) lactate dehydrogenase (LDH), total bilirubin, urea, total protein, albumin, uric acid, creatine phosphokinase (CPK) and troponin T
Coagulation parameters	prothrombin time (PT), international normalized ratio (INR) where therapeutically indicated and partial thromboplastin time (PTT)
Urinalysis (only at screening and EOT)	nitrite, protein, glucose, ketone bodies, urobilinogen, urine bilirubin, erythrocytes, leucocytes, pH (all by urine dipstick)
Additional lab parameters for screening	hepatitis B surface antigen, hepatitis C antibody, HIV-1 and HIV-2 antibody (all qualitative) urine drug screening, alcohol breath test

These parameters will be assessed at time points specified in the [flow chart](#). In case of toxicity, adequate and more frequent blood sampling may be performed at the discretion of the investigator. In case of grade 4 neutropenia, blood must be collected seven days after the first occurrence of grade 4 neutropenia at the latest.

In case of pathological findings, further evaluation should be performed and the findings documented.

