5.2.6 Dose reducing volasertib toxicity

Dose reducing volasertib toxicity (DRT) (i.e. unacceptable volasertib toxicity) is defined as:

- Drug related CTCAE Grade 3 or greater non-haematological toxicity (except emesis or diarrhoea responding to supportive treatment; if drug related nausea, vomiting or diarrhea is sufficiently treated but nevertheless of grade ≥ 3 severity, this is considered),
or
- Drug related CTCAE Grade 4 neutropenia for more than 7 days
or
- Drug related CTCAE Grade 4 thrombocytopenia.

Patients who have experienced an unacceptable toxicity are eligible for re-treatment with volasertib at a reduced dose of volasertib as per [section 4.1.3.1](#).

The maximum tolerated dose of co-administration of itraconazole and volasertib (MTD) is defined as the highest dose for which the incidence of DRT is no more than 1 out of 6 patients.

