As stated in the CTP, in case the tolerable dose of volasertib is less than the initial dose level 300mg, dose would be included as a covariate in the ANOVA model. However, as a consequence of immediate dose de-escalation after first three patients treated on 300mg and two of them discontinued after cycle 1, tolerable dose was de-escalated to 250mg and all subsequently enrolled patients were treated on 250mg. Due to the limited dose levels and sparse data available on 300mg, instead of including dose as an additional covariate in the ANOVA model according to the CTP, primary analysis using ANOVA model on log transformed PK endpoints will be performed based on the clean cohort of patients who were treated on equal dose levels (either 250mg or 300mg) throughout both cycles 1 and 2. In addition, a sensitivity analysis will be performed by including the patients with further intra-individual dose reduction from 250mg to 200mg in cycle 2. In the sensitivity analysis, dose proportionality (BI 1230.5, BI 1230.23) will be applied on individuals with dose reduced to 200mg during cycle 2 volasertib mono therapy to rescale the PK measures. However, since dose proportionality was not established for the combination therapy of volasertib + itraconazole, dose normalization will not be applied on the patient who was treated on 300mg in both cycle 1 and 2.

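### Cohort safety reviews are timed to dosing, but the de-escalation rule counts toxicity over the whole first cycle

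*Protocol*

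**What the plan says.** Protocol 7.3.4 plans no formal interim analysis but describes safety reviews: "a review of all data relevant for safety will be performed after the first three patients were included", and then "reviews of safety will be performed after cohorts of three patients have been dosed". For the de-escalation scheme it points to Section 3.1; the detail is in 4.1.3.1.

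Section 4.1.3.1 sets the rule. At 300 mg the dose falls to 250 mg on this condition: "If more than 1 out of 6 patients experiences unacceptable toxicity (DRT, Section 5.2.6) during the first treatment cycle". A fresh count applies at the next level, with a further step down to 200 mg: "If more than 1 out of 6 patients treated at a volasertib dose of 250 mg experiences unacceptable toxicity during the first treatment cycle".

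On pacing, 3.1 and 4.1.3.1 require completion of the cycle only at the start: "Single patients will be treated for the first cycle until three patients have completed the first cycle". After that, patients come in cohorts of three until preliminary safety is confirmed. No observation period is stated, and nothing holds back further dosing.

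Section 5.2.6 defines the DRTs. They include Grade 4 thrombocytopenia and "Drug related CTCAE Grade 4 neutropenia for more than 7 days". Section 5.2.3 adds that in Grade 4 neutropenia "blood must be collected seven days after the first occurrence of grade 4 neutropenia at the latest".

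SAP 7.4 reports that after three patients at 300 mg the "tolerable dose was de-escalated to 250mg and all subsequently enrolled patients were treated on 250mg".

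**The concern.** The review is tied to an event on Day 1, while the decision it supports rests on an outcome collected to the end of a 21-day cycle. Section 1.2 names reversible suppression of haematopoiesis as volasertib's main side effect, so the toxicity most to be expected is the kind that shows late.

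A review held when 7.3.4 says could let the next patients be dosed while the current cohort's DRT status is unknown. The one explicit safeguard, completing cycle 1 first, covered only the three patients at 300 mg. The new 1-of-6 count at 250 mg, and any at 200 mg, has no such safeguard in the text.

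**Working it through.** The plan states no operating characteristics for the rule, so there is no figure to reproduce. The finding rests on the timeline; the probabilities only show its size.

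**Timeline.** Cycle 1 is 21 days. After the pre-dose sample on Day 1, the flow chart schedules the safety laboratory on Day 8 and Day 15; the 24-hour sample is coagulation only. Grade 4 neutropenia first seen on Day 8 counts only if it lasts more than 7 days, and the repeat count may be taken up to seven days later. It is therefore established as a DRT at about Day 8 + 7 = Day 15. None of this exists on the day of dosing.

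**Chance that a trigger is not yet visible.** The trigger is at least 2 DRTs. For n patients with DRT probability p,

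P(≥2 of n) = 1 − (1−p)^n − n·p·(1−p)^(n−1).

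I assume p = 0.20, 0.30 and 0.40.

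| p | n=6 | n=5 | n=4 | n=3 | n=2 |
|---|---|---|---|---|---|
| 0.20 | 0.345 | 0.263 | 0.181 | 0.104 | 0.040 |
| 0.30 | 0.580 | 0.472 | 0.348 | 0.216 | 0.090 |
| 0.40 | 0.767 | 0.663 | 0.525 | 0.352 | 0.160 |

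If u of the patients under review have no visible outcome yet, the chance that full follow-up would trigger but the review does not is P(≥2 of n) − P(≥2 of n−u). At p = 0.30, n = 6, u = 1, this is 0.580 − 0.472 = 0.108.

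| p | Six patients, u=1 | u=2 | u=3 | First three at a level, u=1 | u=2 or 3 |
|---|---|---|---|---|---|
| 0.20 | 0.082 | 0.164 | 0.241 | 0.064 | 0.104 |
| 0.30 | 0.108 | 0.232 | 0.364 | 0.126 | 0.216 |
| 0.40 | 0.104 | 0.242 | 0.415 | 0.192 | 0.352 |

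The last two columns apply because two DRTs in three patients already exceed 1 of 6.

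**Partial visibility.** Suppose three of six patients have completed cycle 1 and half of the newest three patients' eventual DRTs can be seen. Summing two binomial counts, Bin(3, p) and Bin(3, p/2), the chance of at least 2 is 0.222, 0.407 and 0.585. The shortfall against full follow-up is about 0.12, 0.17 and 0.18.

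**Which u applies.** Section 3.3 plans 24 patients in about 12 months: 365/24 = 15.2 days per patient. When patient 6 is dosed, patient 5 is about 15 days past dosing and patient 4 about 30. At even spacing, u is therefore 1 or 2; u = 3 needs a cohort filled together.

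**Patients exposed in the interval.** 21/15.2 = 1.4 over one cycle at planned accrual, or three if the next cohort is filled at once.

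**The case against.** The strongest reply is that 7.3.4 is a summary. The operative rule in 4.1.3.1 counts first-cycle DRTs, so a dose cannot be confirmed without first-cycle data, and the dosing trigger is only an earliest time. The wording of 7.3.4 is loose elsewhere too: it places the first review at inclusion, although 4.1.3.1 has those patients complete the cycle. This reading is possible, and a careful team would adopt it. But no sentence requires waiting or holds further dosing, and the completion condition written for the first three patients is not repeated for later ones. The overall-design figure and the figure in 7.3.4 were not available to me.

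Several points about size do stand:

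- The probabilities describe delay, not a permanent miss, because a later DRT still lowers the dose for subsequent patients.
- At planned accrual patient 5 has had the Day 8 and Day 15 counts, so u = 1 is nearer the truth than u = 2. The same applies to the second patient in a first cohort of three.
- Some DRTs show early. Patients are inpatients to 72 hours with ECGs to 24 hours, and non-haematological Grade 3 events count.
- The SAP calls 250 mg the MTD and reports few reductions to 200 mg in cycle 2. That is not a DRT rate, since discontinuations are left out, but it lends no support to the higher assumed values.
- The scheme steps down from the recommended Phase II dose; it does not escalate into untested doses. Expedited reporting, extra blood counts and individual dose reductions also protect patients.

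**Conclusion.** The concern holds. Followed as written, 7.3.4 places the cohort reviews before the outcome they must count can be known, and nothing elsewhere makes later cohorts finish cycle 1 before the review or before more patients are dosed. At assumed DRT rates of 20%, 30% and 40%, a six-patient review at evenly spaced planned accrual would not yet show a due trigger with probability 0.08–0.16, 0.11–0.23 and 0.10–0.24. The lower ends are the more realistic if two weeks of data are treated as nearly complete follow-up. With a cohort filled together and nothing visible, the values are 0.24, 0.36 and 0.41. These depend on the assumed rates and on how much is visible at review; the textual gap does not. The harm is limited to roughly 1.4 to 3 patients per interval. It should be corrected because it concerns patient safety and is cheap to repair.

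**What to change.** State in 7.3.4, and match in 4.1.3.1, that each cohort review takes place once every patient in the cohort has completed cycle 1 (Day 22) or had a DRT, and that the next cohort is not dosed before that review. Say that this applies at each dose level (300, 250 and 200 mg) until the 1-of-6 criterion has been assessed in six patients. The cost is one or two sentences and a pause of up to about three weeks per run-in cohort. Because the SAP already treats 250 mg as the MTD, the trial report should also give the date of each review against cycle 1 completion for the patients reviewed.

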7.3.5 Pharmacokinetic analyses

Refer to [Section 7.3.1](#), [7.3.2.1](#) and 7.3.8 for primary, secondary [REDACTED]
analyses.

[figure not shown]
7.3.6 Biomarkers, pharmacodynamic analyses and pharmacokinetic – pharmacodynamic relationship

This section is not applicable in this study.

7.3.8 Other analyses

Preliminary therapeutic effects of volasertib based on the investigator response assessment will be summarised descriptively.

Physical examination data will be summarised descriptively.

Demographics, tumour history as well as concomitant diagnoses and/or therapy will be summarised descriptively.

Proprietary confidential information.

© 2017 Boehringer Ingelheim International GmbH or one or more of its affiliated companies. All rights reserved.
This document may not - in full or in part - be passed on, reproduced, published or otherwise used without prior written permission.

7.4 HANDLING OF MISSING DATA

7.4.1 Safety

With respect to safety evaluations, it is not planned to impute missing values.

7.4.2 Plasma concentration - time profiles

Concentration data identified with NOS (no sample), NOR (no valid result), NOA (not analyzed), BLQ (below the limit of quantification), and NOP (no peak detectable) will be ignored and not replaced by zero at any time point (applies also to the lag phase). Descriptive statistics of concentrations at specific time points will be calculated only when at least 2/3 of the individuals have concentrations within the validated concentration range. The overall sample size to decide whether the “2/3 rule” is fulfilled will be based on the total number of samples intended to be drawn for that time point (i.e. BLQ, NOR, NOS, NOA, NOP are included).

7.4.3 Pharmacokinetic parameters

In the non-compartmental analysis, concentration data identified with NOS, NOR, and NOA will not be considered. BLQ and NOP values in the lag phase will be set to zero. The lag phase is defined as the period between time zero and the first time point with a concentration above the quantification limit. All other BLQ/NOP values of the profile will be ignored.

Every effort will be made to include all concentration data in an analysis. If not possible, a case to case decision is required whether the value should only be excluded from half-life estimation or the complete analysis.

- If a concentration is only excluded from half-life determination, it will be used for all other calculations (e.g. descriptive statistics) and for graphical presentation.
- If a concentration value is excluded from all calculations, it will not be presented graphically or used for the calculation of descriptive statistics and parameter determination. However the excluded concentration itself will be listed in the tables in section 15 of the clinical trial report associated with an appropriate flag.

Descriptive statistics of parameters are calculated only when at least 2/3 of the individual parameter estimates of a certain parameter are available. If the actual sampling time will not be recorded or will be missing for a certain time point, the planned time will generally be used for this time point instead. PK parameters which cannot be determined will be identified by "not calculated" (NC).

Proprietary confidential information.

© 2017 Boehringer Ingelheim International GmbH or one or more of its affiliated companies. All rights reserved.
This document may not - in full or in part - be passed on, reproduced, published or otherwise used without prior written permission.

7.4.4 Efficacy

With respect to efficacy evaluations, it is not planned to impute missing values.

